10.4.3. Total Vaccinated cohort for re-vaccination phase

The Total Vaccinated Cohort (TVC) will include all subjects vaccinated with HZ/su in the ZOSTER-060 study.

The TVC for analysis of immunogenicity will include subjects vaccinated with HZ/su in the ZOSTER-060 study for whom immunogenicity data are available.

The TVC for analysis of safety will include all subjects with at least one HZ/su administration in the ZOSTER-060 study documented.

10.4.3.1. According-to-protocol (ATP) cohort for analysis of immunogenicity

The ATP cohort for analysis of immunogenicity will include all evaluable subjects from the TVC:

- Who meet all eligibility criteria.
- Who have received one or two doses of re-vaccination schedule up to the time point considered.
- For whom administration site of study vaccine is known/ and correct, as per protocol.
- Who have not received any vaccine forbidden in the protocol up to the timepoint considered.
- Who comply with the procedures and intervals defined in the protocol up to the timepoint considered.
- Who did not receive a medication/ product leading to exclusion from the ATP analysis (see Section 6.6.2) up to the timepoint considered.
- Who did not present with an intercurrent medical condition (including herpes zoster) leading to elimination from the ATP analysis (see Section 6.7) up to the timepoint considered.
- Who complied with the vaccination schedule up to the timepoint considered.
- Who complied with the blood sample schedule up to the timepoint considered.
- Who had immunogenicity results available up to the timepoint considered.

Subjects who experience an episode of suspected HZ up to the considered time point of study ZOSTER-060 will be eliminated from the ATP cohort for immunogenicity subsequent to that time point. These subjects will be analysed separately.

10.5. Derived and transformed data

10.5.1. Handling of missing data

- For the analysis of solicited symptoms, missing or non-evaluable measurements will not be replaced. Therefore, the analysis of the solicited symptoms based on the TVC will include only subjects/doses with documented safety data (i.e. symptom screen completed).
- For the analysis of unsolicited symptoms/SAEs/pIMDs/concomitant medication, all vaccinated subjects will be considered and subjects who did not report an event will be considered as subjects without an event.
- For the analysis of immunogenicity, missing or non-evaluable measurements will not be replaced. Therefore, a subject will be excluded from an analysis timepoint if any measurements are missing or non-evaluable for that timepoint.

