10.7.3. Assessment of persistence (Post re-vaccination)

Persistence data will be analyzed at Month 134 (i.e. 12 months after last dose of re-vaccination) timepoint after re-vaccination.

The analysis of antibody persistence (post re-vaccination) at Month 134 will be based on the ATP cohort for analysis of immunogenicity at month 134. If the percentage of subjects who come back for this follow-up with serological results excluded from the ATP cohort is higher than 5%, a second analysis based on the Total Vaccinated Cohort at Month 134 will be performed to complement the ATP analysis.

Humoral immune response endpoint:

For the humoral immune response, if a blood sample is available at Month 134, the following parameters (with 95% CIs) will be tabulated overall and by age group (60-69, ≥ 70 YOA at time of initial vaccination in study ZOSTER-003):

- GMC of anti-gE Ab with 95% CI;
- Humoral seropositivity rate with 95% CI;
- Vaccine response rates [Month 134 over pre-vaccination in the initial study] with 95% CI;
- The geometric mean of the ratio Month 134 over Visit Month 0 (Month 120), in the current study with 95% CI;

- The geometric mean of the ratio Month 134 over pre-vaccination in the initial study with 95% CI;
- The distribution of antibody titres will be tabulated and also presented using reverse cumulative curves.

CMI endpoint:

For CMI response, the following parameters (for gE specific CD4[2+] frequency and CD4[+2] T-cell following induction with gE) will be tabulated overall and by age group (60-69, ≥ 70 YOA at time of initial vaccination in study ZOSTER-003) at M134 (12 months after last dose of re-vaccination):

Descriptive statistics (N, mean, SD, min, Q1, median, Q3, max) of the following parameters will be tabulated:

- Descriptive statistics of the frequency of CD4+ T-cells secreting at least two activation markers (from among IFN- γ , IL-2, TNF- α , CD40L) for gE-specific stimulation.

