6.2.2. Assessment of re-vaccination phase

The analysis of re-vaccination phase will be based on the ATP cohort for analysis of immunogenicity after re-vaccination. If, the percentage of vaccinated subjects with serological results excluded from the ATP cohort for analysis of immunogenicity after re-vaccination is 5% or more, a second analysis based on the TVC will be performed to complement the ATP analysis.

All analyses will be performed overall and by age category at dose 1 of initial vaccination in ZOSTER-003 (60-69, ≥ 70 YOA) if the number of subjects is sufficient in each stratum.

Humoral Immune response

- At each timepoint that a blood sample is available (at Months 120, 121 and 123) post-re-vaccination, the following parameters will be tabulated overall and some by age category at dose 1 of initial vaccination in ZOSTER-003 (60-69, ≥ 70 YOA):
 - GMCs of anti-gE Ab with 95% confidence interval (CIs);
 - Anti-gE seropositivity rates with exact 95% confidence interval (CIs);
 - Vaccine response rates [post re-vaccination (M121 and M123) over pre-vaccination in the initial ZOSTER-003 study] with 95% confidence interval (CIs);
 - MGI (geometric mean of the ratio) Post Month 1 (Month 121) and post Month 3 (Month 123) post re-vaccination (current study) over Pre-re-vaccination (Month 120), with 95% CI;
 - Descriptive statistics of the fold increase over pre-re-vaccination at months 121 and 123 (mean, standard deviation, min, Q1, median, Q3, max).
 - Distribution of the fold increase over pre-re-vaccination at months 121 and 123
 - MGI (geometric mean of the ratio) Post Month 1 (Month 121) and post Month 3 (Month 123) post re-vaccination (current study) over pre-vaccination in the initial ZOSTER-003 study, with 95% CI;
- The distribution of antibody titers at Months 120, 121 and 123 will be presented using reverse cumulative curves.

CMI response

- Descriptive statistics (N, mean, SD, min, Q1, median, Q3, max) for the following parameters will be tabulated at Months 120, 121 and 123 overall and some by age category at dose 1 of initial vaccination in ZOSTER-003 [60-69, \geq 70 YOA]:
 - the frequency of gE specific CD4+T-cells secreting at least 2 activation markers (among IFN- γ , IL-2, TNF- α , CD40L)
 - the frequency of CD4+ T-cells following induction with gE secreting at least 2 activation markers (among IFN- γ , IL-2, TNF- α , CD40L)
 - the fold increase over pre-re-vaccination in the frequency of gE specific CD4[2+] T-cells at months 121 and 123

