6.2.3. Assessment of persistence after re-vaccination

Persistence data will be analyzed at Month 134 timepoint after re-vaccination (i.e. 12 months after last dose of re-vaccination).

The analysis of antibody persistence after re-vaccination at Month 134 will be based on the ATP cohort for analysis of immunogenicity at Y11. If the percentage of subjects who come back for this follow-up with serological results excluded from the ATP cohort is higher than 5%, a second analysis based on the TVC for revaccination course will be performed to complement the ATP analysis.

Humoral immune response:

- If a blood sample is available at Month 120, 121, 123 and 134, the following parameters (with 95% CIs) will be tabulated overall and some by age group (60-69, ≥ 70 YOA at time of initial vaccination in study ZOSTER-003):
 - GMCs of anti-gE Ab with 95% confidence interval (CIs);
 - Anti-gE seropositivity rates with exact 95% confidence interval (CIs);
 - Vaccine response rates [post re-vaccination over pre-vaccination in the initial ZOSTER-003 study] with 95% confidence interval (CIs);
 - MGI (geometric mean of the ratio) post re-vaccination (current study) over Pre-re-vaccination (Month 120), with 95% CI;
 - Descriptive statistics of the fold increase over pre-re-vaccination at months 121, 123 and 134 (mean, standard deviation, min, Q1, median, Q3, max).
 - Distribution of the fold increase over pre-re-vaccination at months 121, 123 and 134
 - MGI (geometric mean of the ratio) post re-vaccination (current study) over pre-vaccination in the initial ZOSTER-003 study, with 95% CI;
- The distribution of antibody titers at Months 121, 123 and 134 will be presented using reverse cumulative curves.

CMI response:

- Descriptive statistics (N, mean, SD, min, Q1, median, Q3, max) for the following parameters will be tabulated at Months 120, 121, 123 and 134 overall and some by age category at dose 1 of initial vaccination in ZOSTER-003 [60-69, ≥ 70 YOA]:
 - the frequency of gE specific CD4+T-cells secreting at least 2 activation markers (among IFN- γ , IL-2, TNF- α , CD40L)
 - the frequency of CD4+ T-cells following induction with gE secreting at least 2 activation markers (among IFN- γ , IL-2, TNF- α , CD40L)
 - the fold increase over pre-re-vaccination in the frequency of gE specific CD4[2+] T-cells at months 121, 123 and 134
 - the fold increase over pre-re-vaccination in the frequency of CD4[2+] T-cells following induction with gE at months 121, 123 and 134

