7.2. Handling of missing data

7.2.1. Immunogenicity

For a given subject and a given immunogenicity measurement, missing or non-evaluable measurements will not be replaced. Therefore, analyses will exclude subjects with missing or non-evaluable measurements.

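### Protocol 10.5.1 literally drops a valid ELISA result when the ICS result at the same visit is missing, in conflict with SAP 7.2.1; separately, SAP 6.2.3 can be read as a four-visit completeness condition

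*Protocol*

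**What the plan says.** Protocol 10.5.1 gives one missing-data rule for the analysis of immunogenicity as a whole. Missing or non-evaluable results are not replaced, and as a consequence "a subject will be excluded from an analysis timepoint if any measurements are missing or non-evaluable for that timepoint". The unit of exclusion is the timepoint. The trigger is not limited to one assay.

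SAP 7.2.1 (Amendment 1) frames the rule differently: "For a given subject and a given immunogenicity measurement, missing or non-evaluable measurements will not be replaced". Its next sentence excludes subjects with missing or non-evaluable measurements, so it points to assay-by-assay exclusion without saying so outright. SAP section 9, on changes from planned analyses, is marked NA.

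For the humoral tables after re-vaccination, SAP 6.2.3 opens with "If a blood sample is available at Month 120, 121, 123 and 134, the following parameters (with 95% CIs) will be tabulated overall". The matching text in Protocol 10.7.3 sets a condition on one visit only: "For the humoral immune response, if a blood sample is available at Month 134". SAP 6.2.2, on the same phase up to Month 123, uses per-timepoint wording: "At each timepoint that a blood sample is available (at Months 120, 121 and 123) post-re-vaccination". The CMI list in SAP 6.2.3 names the same four months with no availability condition.

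**The concern.** ELISA and ICS results can fail independently. Protocol 5.6.9.1 draws about 5 mL of blood for serum, which is frozen, and a separate sample of about 20 mL, which is shipped at room temperature for cell separation within 24 hours. Tables 7 and 8 assign the two assays to different laboratories, and Appendix A has ICS run on thawed cells. Table 9 lists both read-outs at every sampling visit. Under the literal 10.5.1 rule, a lost or non-evaluable cell sample would delete a sound antibody result, which costs precision on a primary endpoint for a reason unrelated to the antibody assay.

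The second issue is separate. It acts across visits rather than within one, and it concerns only the humoral tables after re-vaccination. If the months in SAP 6.2.3 are taken as a joint condition, a subject who missed one of the four samples would leave the antibody tables at all of them.

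In both cases two competent programmers could produce different antibody counts, GMCs and MGIs from the same data. The study is descriptive, so these estimates and their intervals are the result.

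**Working it through.** The plan has no figure to reproduce: it states no assay-failure rate, dropout rate, standard deviation or precision target. Protocol Table 1 gives about 100 subjects. The rates below are assumptions.

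**Within a visit (Protocol 10.5.1).** Let c be the share of ICS results missing or non-evaluable at a visit, independent of the ELISA result. Exclusion by assay keeps every valid ELISA result. The literal rule keeps a fraction 1 − c of them. Confidence-interval width on the log scale changes by about 1/√(1 − c), ignoring the small change in the t quantile.

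| Assumed c | Valid ELISA results lost | Width factor |
|---|---|---|
| 5% | 5% | 1/√0.95 = 1.026 |
| 10% | 10% | 1/√0.90 = 1.054 |
| 20% | 20% | 1/√0.80 = 1.118 |

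The range is a loss of 5% to 20% and intervals about 3% to 12% wider. The same argument applies to valid ICS results when an ELISA result fails.

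**Across visits (SAP 6.2.3 read as all four samples required).** Let m be the loss per visit, independent between visits. A per-timepoint rule keeps 1 − m of subjects at each visit. The four-visit rule keeps (1 − m)^4. The ratio is (1 − m)^3, and the width factor is 1/√[(1 − m)^3].

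| Assumed m | Per-timepoint | All four visits | Ratio | Width factor |
|---|---|---|---|---|
| 5% | 0.95 | 0.95^4 = 0.815 | 0.95^3 = 0.857 | 1.080 |
| 10% | 0.90 | 0.90^4 = 0.656 | 0.90^3 = 0.729 | 1.171 |

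Intervals would be about 8% to 17% wider than under a per-timepoint rule. Independence is the unfavourable case. If loss is monotone dropout, everyone with a Month 134 sample also has the three earlier ones. Month 134 then loses nobody, and the earlier months lose only those who drop out later.

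**Reach.** Protocol 10.5.1 applies to all immunogenicity timepoints, so it reaches the primary endpoints in Protocol 10.1. SAP 6.2.3 starts at Month 120 as the pre-re-vaccination value and feeds only the re-vaccination tables. The primary persistence analysis is in SAP 6.2.1, and its cohort in Protocol 10.4.2 asks for results at the considered timepoint only.

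**The case against.** The strongest reply is that no data need be lost. SAP 7.2.1 speaks of a given measurement, as did the superseded SAP version 1. Protocol 10.7.1 and 10.7.2 tabulate antibody results wherever a sample exists at that timepoint. On this view 10.5.1 is only loosely worded. That stands as evidence of likely intent, so a reader who infers that valid antibody results will in fact be discarded goes further than the documents allow. It does not remove the conflict. The protocol sentence covers both assays, nothing records that it was replaced, and Protocol 10.10 requires changes from its statistical plan to be described and justified.

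A reader might also infer that SAP 6.2.3 requires all four samples. The documents do not settle this. The months can equally be the columns of the final table, the parallel CMI item uses them that way, and the SAP history says the amendment made no major change. Against that, the re-vaccination ATP cohort in Protocol 10.4.3.1 includes those "Who had immunogenicity results available up to the timepoint considered", which leans towards needing earlier visits too. The wording is ambiguous, and no more can be claimed.

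Three further inferences are not supported:

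- Comparing 0.815 and 0.656 with complete data gives intervals 11% to 23% wider. That is the wrong comparator, because 5% to 10% would be missing at each visit under either rule.
- Nothing in the documents shows that ICS fails more often in frailer subjects, so selection bias in the antibody sample is conjecture.
- Different subject sets for antibody and CMI are not in themselves a fault. Exclusion by assay produces them too, while the literal 10.5.1 rule would align them within a visit.

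Finally, the complementary analysis, triggered at 5% or more ATP exclusions (more than 5% at Month 134), might recover some results. It is not a sure remedy: the trigger counts exclusions from the ATP cohort, whereas 10.5.1 excludes from a timepoint and is not limited to that cohort, so the same losses could recur in the second analysis.

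**Conclusion.** The point holds as a conflict between protocol and SAP, plus a separate ambiguity in the SAP. As written, Protocol 10.5.1 removes a valid ELISA result when the ICS result at the same visit is missing, and the reverse, at all immunogenicity timepoints including the primary ones. SAP 7.2.1 points the other way, and the difference is not recorded. SAP 6.2.3 admits a four-visit reading that Protocol 10.7.3 and SAP 6.2.2 do not share, without consequence for the primary endpoints.

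The true size is unknown. The calculated ranges rest on the assumed failure rates and on independence, and the two mechanisms should not be added together as though both were established. No pre-specified test or decision depends on the outcome. What is at stake is precision and an unambiguous N, which justifies a correction at this cost.

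**What to change.** In Protocol 10.5.1, replace the exclusion sentence with a rule by assay and timepoint: a subject leaves the analysis of an assay at a timepoint only when that assay's own result there is missing or non-evaluable; a within-subject ratio needs both results of that assay. This agrees with the per-measurement wording of SAP 7.2.1.

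In SAP 6.2.3, replace the opening condition with the per-timepoint formula of SAP 6.2.2, listing Months 120, 121, 123 and 134.

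The cost is two sentences. N will differ slightly between assays and between timepoints, so each table should show its own N.

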10.5.2. Humoral immune response

A seronegative subject is a subject whose Ab concentration is below the cut-off value.

A seropositive subject is a subject whose Ab concentration is greater than or equal to the cut-off value.

The seropositivity rate is defined as the percentage of seropositive subjects.

The Vaccine Response Rate (VRR) for anti-gE is defined as the percentage of subjects who have at least:

- a 4-fold increase in the anti-gE Ab concentration as compared to the pre-vaccination anti-gE Ab concentration, for subjects who are seropositive at baseline, or,
- a 4-fold increase in the anti-gE Ab concentration as compared to the anti-gE Ab cut-off value for seropositivity, for subjects who are seronegative at baseline.

Note: Baseline is the pre-vaccination titre in the initial study ZOSTER-003.

The GMC calculations are performed by taking the anti-log of the mean of the log concentration transformations. Ab concentrations below the cut-off of the assay will be given an arbitrary value equal to half the cut-off for the purpose of GMC calculation.

The Mean Geometric Increase (MGI) is defined as the geometric mean of the within subject ratios of the post-vaccination titre to the Day 0 titre (pre-vaccination titre in the initial study).

10.5.3. CMI response

For the descriptive analyses, the frequency of CD4[2+] T-cells upon in vitro stimulation with the gE-antigen (induction condition) is calculated by dividing the number of activated CD4[2+] T-cells (numerator) over the total number of CD4 T-cells involved (denominator). The same calculation will be performed for the frequency computation for any kinds of cells and for each individual activation marker as appropriate.

$$Freq_{CD4[2+]} = \frac{n_{Induction}^{2+}}{N_{CD4}}$$

$n_{Induction}^{2+}$ = number of CD4 T – cells secreting at least 2 activation markers after induction with the antigen

N_{CD4} = Total number of CD4 T – cells involved in the assay (induction)

The frequency of gE-specific CD4 T-cells for each individual subject is calculated as the difference between the frequency of CD4[2+] T-cells, upon in vitro stimulation with the gE antigen (induction condition) minus the frequency of CD4[2+] T-cells upon in vitro stimulation in medium only (background condition). The differences less or equal to one are imputed to one gE-specific CD4[2+] T-cell per 10^6 CD4+ T-cells. The same calculation will be performed for the frequency computation for any kind of cells and for each individual activation marker as appropriate.

$$Freq_{Specific}^{CD4[2+]} = \frac{n_{Induction}^{2+}}{N_{Induction}^{CD4}} - \frac{n_{Background}^{2+}}{N_{Background}^{CD4}}$$

$$if \frac{n_{Induction}^{2+}}{N_{Induction}^{CD4}} > 1 + \frac{n_{Background}^{2+}}{N_{Background}^{CD4}}$$

$$Freq_{Specific}^{CD4[2+]} = 1$$

$$if \frac{n_{Induction}^{2+}}{N_{Induction}^{CD4}} \leq 1 + \frac{n_{Background}^{2+}}{N_{Background}^{CD4}}$$

$n_{Induction}^{2+}$ = number of CD4 T - cellssecreting at least 2 activation markers after induction with the gE - antigen

$n_{Background}^{2+}$ = number of CD4 T - cellssecreting at least 2 activation markers in the medium conditions

N^{CD4} = Total number of CD4 T - cellsinvolved in the assay (induction of background)

- The GM frequency calculations are performed by taking the anti-log of the mean of the log frequency transformations.
- The CMI vaccine response to gE will be based on the gE-specific data as computed above. The lower limit of linearity (LLL) for the assay will be used as threshold for vaccine response assessment and the estimated value will be detailed in the Statistical Analysis Plan (SAP). The Vaccine Response (VR) is defined as the percentage of subjects who have:
 - at least a 2-fold increase as compared to the LLL, for subjects with pre-vaccination T-cell frequencies below the LLL;
 - at least a 2-fold increase as compared to pre-vaccination T-cell frequencies, for subjects with pre-vaccination above the LLL.

10.6. Analysis of demographics

The analysis of demography for the persistence phase at Month 108 and Month 120 post first dose of initial vaccination course will be performed on the Total enrolled cohort and the ATP cohort for persistence.

- Demographic characteristics (age at Month 108 and Month 120 persistence phase respectively, gender, geographic ancestry, race and ethnicity), cohort description and withdrawal status will be summarized overall.
- The mean age at Month 108 and Month 120 (plus range and standard deviation) of the enrolled subjects, as a whole, and stratified by age group will be calculated.
- The distribution of subjects enrolled among the study sites will be tabulated.
- Frequency tables will be generated for categorical variables such as gender.
- Mean, median and standard error will be provided for continuous data such as age.

The analysis of demography for the re-vaccination phase will be performed on the Total vaccinated cohort and ATP cohort for immunogenicity.

- Demographic characteristics (age at first re- vaccination dose, gender, geographic ancestry, race and ethnicity), cohort description and withdrawal status will be summarized overall.
- The mean age at first study re-vaccination dose (plus range and standard deviation) of the enrolled subjects, as a whole, and stratified by age group will be calculated.
- The distribution of subjects enrolled among the study sites will be tabulated.

- Frequency tables will be generated for categorical variables such as gender.
- Mean, median and standard error will be provided for continuous data such as age.

10.7. Analysis of immunogenicity

10.7.1. Assessment of follow-up of persistence phase Months 108 and 120 post first dose of initial vaccination course.

The analysis for the persistence phase at Month X (Month 108 and Month 120) post first dose of initial vaccination course will be performed on the ATP cohort for persistence at Month X – adapted for each time point. If, the percentage of subjects with serological results excluded from the ATP cohort for analysis of persistence is 5% or more, a second analysis based on the Total enrolled cohort will be performed to complement the ATP analysis.

All analyses will be performed overall and by age stratum if the number of subjects is sufficient in each stratum.

Humoral Immune response endpoint

For the humoral immune response, at each timepoint that a blood sample is available (at Months 0, 3, 12, 24, 36, 48, 60, 72, 108 and 120) post initial vaccination, the following parameters (with 95% CIs) will be tabulated overall, and by age group:

- Geometric mean concentrations (GMCs) of anti-gE Ab with 95% confidence interval (CIs).
- Humoral seropositivity rates with exact 95% confidence interval (CIs);
- Descriptive statistics of the fold over pre-vaccination in the initial study at months 3, 12, 24, 36, 48, 60, 72, 108 and 120 (Mean, Standard deviation, Min, Q1, Median, Q3, Max).
- The geometric mean of the ratio Post month x over pre-vaccination in the initial study with 95% CI.
- The distribution of antibody titres will be tabulated and also presented using reverse cumulative curves.

CMI endpoint

For CMI response, the following parameters (for gE specific CD4[2+] frequency and CD4[+2] T-cell following induction with gE) will be tabulated overall and by age group [60-69,>=70 YOA at time of initial vaccination in study ZOSTER-003] at Months 0, 3, 12, 24, 36, 48, 60, 72, 108 and 120 post first dose of initial vaccination:

Descriptive statistics (N, mean, SD, min, Q1, median, Q3, max) of the following parameters will be tabulated:

- Descriptive statistics of the frequency of CD4+ T-cells secreting at least two activation markers (from among IFN- γ , IL-2, TNF- α , CD40L) for gE-specific stimulation.
- Descriptive statistics of the fold over pre-vaccination in the initial study at months 3, 12, 24, 36, 48, 60, 72, 108 and 120.

Exploratory analysis

A piece-wise linear mixed model and modified power law model for repeated measurements (all data available from month 0, 3, 12, 24, 36, 48, 60, 72, 108 and 120 post first dose of initial vaccination) will be used to model over time the frequency of CD4 T-cells producing at least 2 immunological activation markers following stimulation with gE [Ledent, 2009] and gE antibody concentrations. The covariates for the frequency of CD4 T-cells will include background CD4 frequency, log transformed prevaccination response and the log-transformed of the time elapsed (measured in months) following the initial vaccination. The covariates for the anti-gE will include log transformed prevaccination response. The model allows for random individual deviations from the overall mean response (random intercept) and, if necessary according to Schwarz' Bayesian Information Criterion (SBIC) and Akaike's Information Criterion (AIC) goodness-of-fit statistics, for a random individual deviation from the overall CD4-frequency decay over time (random coefficient [slope]).

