3.2. Secondary objectives

For the persistence phase Months 108 and 120 post first dose of initial vaccination in study ZOSTER-003:

- To evaluate the persistence of humoral and cell-mediated immune responses within each age cohort (60-69 YOA and ≥ 70 YOA at the time of the initial vaccination) at Months 108 and 120 post first dose of initial vaccination course.
- To evaluate the safety of the study vaccine from Months 108 to Months 120 post first dose of initial vaccination course.

For the re-vaccination phase:

- To evaluate humoral and cell-mediated immune responses to a two dose re-vaccination course at one month after each dose (Months 121 and 123) and 12 months after last dose (Month 134) when administered 10 years after the initial vaccination course.
- To evaluate the reactogenicity and safety of the study vaccine after re-vaccination with two additional doses.

Refer to Section [4.2](#) for the definition of the secondary endpoints.

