6.2. Analysis of immunogenicity

6.2.1. Assessment of follow-up of persistence phase Months 108 and 120 after initial vaccination course.

The analysis for the persistence phase at Month 108 and Month 120 after initial vaccination course will be performed on the ATP cohort for immunogenicity at Y9 and ATP cohort for immunogenicity at Y10. If, the percentage of subjects with serological results excluded from the ATP cohort for analysis of persistence is 5% or more, a second analysis based on the total enrolled cohort will be performed to complement the ATP analysis. All analyses will be performed overall and by age category at dose 1 of initial vaccination in ZOSTER-003 if the number of subjects is sufficient in each stratum.

The exploratory analysis of modelling the persistence of immune response (humoral and cellular) after initial vaccination will be performed on subjects who received two doses of HZ/su vaccine in ZOSTER-003.

Humoral Immune response

- At each timepoint that a blood sample is available (at Months 0, 3, 12, 24, 36, 48, 60, 72, 108 and 120) post initial vaccination, the following parameters will be tabulated overall, and some by age category at dose 1 of initial vaccination in ZOSTER-003:
 - Geometric mean concentrations (GMCs) of anti-gE Ab with 95% confidence interval (CIs);
 - Anti-gE seropositivity rates with exact 95% confidence interval (CIs);
 - Descriptive statistics on Anti-gE antibody concentrations (mean, standard deviation, min, Q1, median, Q3, max)
 - Vaccine response rates for anti-gE antibody concentrations
 - Descriptive statistics of the fold increase over pre-vaccination in the initial study at months 3, 12, 24, 36, 48, 60, 72, 108 and 120 (mean, standard deviation, min, Q1, median, Q3, max).
 - Distribution of the fold over pre-vaccination in the initial study at months 3, 12, 24, 36, 48, 60, 72, 108 and 120
 - Mean Geometric Increase (MGI), ie geometric mean of the ratio Post-vaccination at months 3, 12, 24, 36, 48, 60, 72, 108 and 120 over pre-vaccination in the initial study, with 95% CI.
- The distribution of antibody titers at Months 48, 60, 72, 108 and 120 will be presented using reverse cumulative curves.

CMI response

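### Age cohort is missing from the listed covariates of the exploratory persistence models; adding it with its time interaction would cheaply protect the overall ten-year curve from a possible upward drift

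*Protocol*

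**What the plan says.** The exploratory part of Protocol 10.7.1 models anti-gE concentration and CD4 frequency over time, using "all data available from month 0, 3, 12, 24, 36, 48, 60, 72, 108 and 120 post first dose of initial vaccination". For CD4, "The covariates for the frequency of CD4 T-cells will include background CD4 frequency, log transformed prevaccination response" and log time since the initial vaccination. For antibody, "The covariates for the anti-gE will include log transformed prevaccination response". A random intercept is specified. A random slope is added only if the information criteria call for it, and the wording mentions only CD4 decay.

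SAP Amendment 1, section 6.2.1, names three forms (piece-wise linear mixed, power law, modified power law), says the modelling "will be performed on subjects who received two doses of HZ/su vaccine in ZOSTER-003", and lists no covariates or random effects. The planned output is graphical.

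Age cohort (60-69 or ≥70 at first dose) is a defined subgroup in SAP section 2 and the basis of a secondary objective: "To evaluate the persistence of humoral and cell-mediated immune responses within each age cohort". Both documents also have a by-age rule. The protocol says "All analyses will be performed overall and by age stratum if the number of subjects is sufficient in each stratum". The SAP says "All analyses will be performed overall and by age category at dose 1 of initial vaccination in ZOSTER-003", under the same condition on numbers.

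**The concern.** A mixed model fitted to incomplete follow-up is valid under missing-at-random only given what it conditions on. Suppose loss to follow-up depends on age and age also affects the rate of waning. Then leaving age out breaks that condition. A random intercept absorbs an age difference in level, but not a difference in slope. The late part of the curve would then lean towards the younger subjects who remain.

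Both conditions are plausible. The study reaches only those still available nine years after vaccination at 60 or older, withdrawals are not replaced (Protocol 9.2), and missing results are not imputed (SAP 7.2.1). Protocol 1.1 itself links ageing to loss of VZV-specific T-cell responses. Neither condition is quantified. At stake is whether the overall modelled curve describes everyone who received two doses or a younger-weighted group.

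**Working it through.** **Plan's own figure.** There is none to reproduce. The documents give no sample size calculation, no waning or dropout by age, and no model-based Month 120 estimate. The one relevant number is about 100 subjects foreseen (Protocol section 3, Table 1).

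**Inputs.** From the documents: visit months, covariates, model forms, about 100 subjects. Assumed: 160 original two-dose recipients, the age mix, retention by age, the waning gap and the variances.

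**Hand formula.** Let p be the share of ≥70 among all recipients, s their share among those retained, and d the extra loss of the ≥70 cohort by Month 120 in natural logs. If the late curve took nothing from earlier visits, then

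bias = exp[(p − s) × d] − 1.

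It is zero if d = 0 or s = p, so both conditions are needed.

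- *About 100 retained, small gap.* With p = 2/3 and 70% retention in 60-69, 100 subjects require (100 − 160×⅓×0.70)/(160×⅔) = 62.7/106.7 = 59% in ≥70. Then s = 62.7/100 = 0.627 and p − s = 0.040. For extra losses of 0.05, 0.10 and 0.15 log10 (each × 2.303), bias is 0.5%, 0.9% and 1.4%.
- *About 100 retained, wider gap.* Retention 80% and 53%: 42.7 + 56.5 = 99.2 subjects, s = 0.570, p − s = 0.097. Bias is 1.1%, 2.3% and 3.4%.

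**Simulation 1.** Piece-wise model with random intercept and slope, variances treated as known, two thirds ≥70, 1,500 data sets per scenario:

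| Retention 60-69 / ≥70 | Bias, extra loss 0.05 to 0.15 log10 | Coverage of 95% CI |
|---|---|---|
| 70% / 59% | +0.4%, +0.8%, +1.0% | 94.6-95.2% |
| 80% / 53% | +0.8% to +3.0% | 91.5-94.1% |

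With retention of 70% against 35% or 25%, bias at 0.10 log10 is +3.5% or +5.4%. Those cases keep only 37.3 + 37.3 = 75 or 37.3 + 26.7 = 64 subjects, below the 100 foreseen.

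**Simulation 2.** REML fits, 1,000 data sets per scenario, half the 160 recipients ≥70. Log-scale SDs: intercept 0.65, slope 0.30 by Month 120, residual 0.35. Level ratio means ≥70 over 60-69 at Month 120 due to waning. Cells show bias (coverage):

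| Level ratio; dropout 60-69 / ≥70 | Piece-wise, random slope | Piece-wise, intercept only | Power law, random slope |
|---|---|---|---|
| 0.75; 30% / 50% | +1.4% (94.3%) | +1.7% (91.2%) | +0.4% (95.0%) |
| 0.75; 20% / 70% | +4.2% (89.5%) | +4.8% (83.8%) | +1.3% (93.1%) |
| 0.60; 30% / 60% | +4.3% (91.3%) | +5.2% (83.5%) | +1.2% (94.4%) |
| 0.50; 20% / 70% (extreme) | +10.0% (73.5%) | +12.4% (50.9%) | +2.6% (93.7%) |

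The first row retains 96 subjects and the others 88. One piece-wise run with 70% of recipients ≥70 (ratio 0.60, dropout 20%/70%, 72 retained) gave +7.2% with a random slope.

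**Controls.** With dropout alone or waning alone differing by age, bias is −0.1% to −0.2%. The intercept-only model covers only 92.0-93.4% even then, so part of its shortfall comes from the missing random slope.

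**Repair.** With age cohort and age-by-time, averaged over the original age mix, bias is −0.1% to −0.3% and coverage 94.3-95.4% in every Simulation 2 scenario. The modified power law was not tested.

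**The case against.** **Age may already be handled.** Read literally, the by-age rule covers the models, and separate fits carry the same information as an interaction. Age-specific geometric means are planned too, so the secondary objective does not rest on these models. This stands in part. The rule depends on sufficient numbers and, even if applied, leaves the overall curve a pooled fit.

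**The target is a choice.** SAP 6.2.1 names an analysis set; it does not define an average standardised to the original age mix. That is correct. The fix therefore asks for the target to be stated.

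**The effect is small.** With about 100 of an assumed 160 retained, a modest retention gap gives 1% or less. The models are exploratory, the analyses are descriptive, and no decision rule uses the curve. All of this stands and sets the low priority.

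**Stronger readings.** A reader might infer that the interval under-covers as a rule. The documents do not support this: no model-based interval is specified, and SAP 7.4 gives methods only for proportions and geometric means. With a fitted random slope and mild gaps, coverage is near nominal because the unmodelled age effect widens the slope variance. A reader might also infer that loss to follow-up is known to depend on age. The documents give no rate, overall or by age, so it is only a possibility.

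**Conclusion.** The point holds as a cheap improvement to an exploratory analysis. Age cohort is absent from the covariates the protocol lists, the SAP lists none, and the by-age rule does not correct the overall curve. If the ≥70 cohort both wanes faster and is lost more often, the piece-wise curve with random slope overstates the Month 120 level by about 0.4% to 3% when about 100 of 160 are retained. With larger gaps in retention or waning the figure is about 4% to 5%; only the extreme combinations go higher. The plain power law is less affected. With only one of the two conditions, there is no bias. Under-coverage of any model-based interval is a risk for large gaps or an intercept-only fit, not a general result. Every size rests on assumed inputs. The primary immunogenicity tabulations do not use these models.

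**What to change.** In Protocol 10.7.1 and SAP 6.2.1, specify for both the anti-gE and CD4 persistence models:

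- Fixed effects: the covariates already listed, plus age cohort at first ZOSTER-003 dose (60-69, ≥70) and its interaction with the time terms. In the power law forms, let the decay differ by cohort. An age main effect alone is not enough.
- Overall curve: the average of the two cohort curves, weighted by the age mix of all two-dose recipients, shown with the two cohort curves from the same fit.
- For clarity, the random effects of the anti-gE model and whether the by-age rule applies to the models.

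The cost is a line or two of text and one term with its interaction per model. No new data are needed. Intervals may widen slightly. In a run of the Simulation 1 design with 250 data sets per scenario, the half-width rose from 11.6-12.1% to 11.8-12.7%, about 0.2 to 0.6 percentage points. In Simulation 2 the mean standard error hardly changed for the mild-gap piece-wise case (0.065 without age, 0.064 with).
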